10.1 METHODS OF ANALYSIS

Response rates will be calculated as the percent of patients whose best response is a CR or PR. Toxicity information recorded will include the type, severity, time of onset, time of resolution, and the probable association with the study regimen. Tables will be constructed to summarize the observed incidence by severity and type of toxicity.

10.2 EVALUATION OF RESPONSE

Any patient who is enrolled and receives at least one full course (4 cycles) of mithramycin will be considered evaluable for response provided: (1) the patient demonstrates progressive disease or death while on protocol therapy; (2) the patient is observed on protocol therapy for at least one course and the tumor is not removed surgically prior to the time complete response or partial response is confirmed; or (3) the patient demonstrates a complete or partial response as confirmed according to protocol criteria. Patients who electively terminate therapy before receiving completing a full course of mithramycin and do not expire within 14 days from start of treatment will be replaced. Patients who experience disease progression after the first course but who did not receive a full course will be taken off-treatment and will only be evaluable for toxicity (not evaluable for response).

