The primary endpoint of the Phase II component study will be evaluated for objective response by RECIST criteria v 1.1. Patients will be enrolled into two cohorts (primary thoracic malignancy; extra-thoracic malignancy metastatic to the chest). The best response to mithramycin will be examined for each cohort. In each cohort, the trial will seek to rule out an unacceptably low 5% objective response rate (ORR; $p_0=0.05$), in favor of a higher response rate of 30% ($p_1=0.30$). With $\alpha=0.10$ (probability of accepting a poor treatment=0.10) and $\beta=0.10$ (probability of rejecting a good treatment=0.10), the study will initially enroll 7 evaluable patients in each cohort and if 0 of the 7 have a response, then no further patients will be accrued in that cohort. If 1 or more of the first 7 in a cohort have a response, then accrual will continue until a total of 21 evaluable patients have enrolled in that cohort. As it may take several weeks to determine if a patient has experienced a response, a temporary pause in the accrual to the trial may be necessary to ensure that enrollment to the second stage is warranted. If there are 1 to 2 responses in 21 patients, this would be an uninterestingly low response rate, while if there were 3 or more responses in 21 patients, then this would be sufficiently interesting to warrant further study of the patients from that cohort in later trials. Under the null hypothesis (5% response rate), the probability of early termination in each cohort is 70%.

The following table summarizes the two stage design that will be used for each cohort in the Phase II component of this trial.

	Cumulative Number of Responses	Decision
Stage 1: Enter 7 patients	0	Terminate the trial: agent ineffective
	1 or more	Inconclusive result, continue trial (proceed to Stage 2)
Stage 2: Enter 14 additional patients	2 or less	Terminate the trial: agent ineffective
	3 or more	Terminate the trial: agent effective

With two cohorts, up to 42 evaluable patients may be required to be accrued to the Phase II portion. It is expected that 10-15 patients per year may enroll onto this study. Thus, 2 to 3 years may be needed to enroll up to 15 patients in Phase I plus 36 evaluable patients in Phase II (up to 6 patients may continue from the Phase I component of the trial). This may be completed much sooner depending on the number actually required. To allow for a small number of inevaluable patients, the accrual ceiling will be set at 60.

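### Section 10.2 conflicts with itself on who counts for response and, as worded, drops patients lost before 4 cycles, so the Phase II ORR can overstate the rate among all treated patients

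*Combined protocol and SAP*

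**What the plan says.** Section 10 sets a Simon two-stage design for each Phase II cohort, with a null response rate of 5%, a target of 30%, and alpha and beta of 0.10. The counts are of evaluable patients: "the study will initially enroll 7 evaluable patients in each cohort and if 0 of the 7 have a response", the cohort stops; otherwise "accrual will continue until a total of 21 evaluable patients have enrolled in that cohort". Three or more responses in 21 is a positive result. Section 2.4 also counts evaluable patients. On losses, section 10 says only: "To allow for a small number of inevaluable patients, the accrual ceiling will be set at 60".

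Section 10.2 defines evaluability. Its opening is "Any patient who is enrolled and receives at least one full course (4 cycles) of mithramycin will be considered evaluable for response provided", followed by three alternatives: progression or death on protocol therapy; observation on therapy for at least a course without surgical removal of the tumor; or a confirmed CR or PR. Patients who electively stop before a full course "and do not expire within 14 days from start of treatment will be replaced". The last sentence reads "Patients who experience disease progression after the first course but who did not receive a full course will be taken off-treatment", and adds that they count for toxicity but not for response.

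Section 10.1 does not mention evaluability: "Response rates will be calculated as the percent of patients whose best response is a CR or PR".

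**The concern.** ORR is the Phase II primary endpoint, and it drives both the stop at 0/7 and the success rule of 3 or more in 21. Read literally, the 4-cycle condition governs all three alternatives, so a patient who deteriorates or dies after two infusions is not evaluable and another patient fills the place.

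The section does not hold together on that reading. If 4 cycles are already required, naming progression or death on therapy adds almost nothing, so that clause looks meant to keep early failures as non-responders. The last sentence describes a patient who progressed after the first course yet did not receive a full course, although a course is 4 cycles.

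Two things are at stake. The reported ORR can exceed the rate among patients who started treatment. And the same patient could be scored as a non-responder or replaced, depending on the sentence applied, possibly with the outcome already known. In a stage of 7, one such choice can decide whether a cohort stops.

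**Working it through.** **Who is lost.** Infusions are 14 days apart (section 3.2), so the fourth starts on Day 1 + 3×14 = 43. Restaging follows the fourth cycle (sections 3.1 and 3.1.2.1), at about Day 56-60, and section 6.3.3.1 does not allow PD to be called before the Day 60 evaluation. A patient who completes 4 cycles on time and then shows radiographic progression therefore stays in as a non-responder. Those who drop out are lost in roughly the first six weeks to clinical progression, deterioration, death, toxicity or withdrawal. They have had no scheduled restaging, and a response also needs confirmation at least 4 weeks later (section 6.3.4). They are therefore almost all non-responders.

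**Effect on the ORR.** With 3 responses in 21 evaluable patients, ORR = 3/21 = 14.3%. If 5 patients were lost and replaced on the way, the all-treated rate is 3/(21+5) = 3/26 = 11.5%.

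**The plan's own design.** Inputs from section 10: n1 = 7, stop at 0; n = 21, success at 3 or more; p0 = 0.05; p1 = 0.30.

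P(success | p) = Σ over x = 1 to 7 of b(7, x, p) × P(Bin(14, p) ≥ 3 − x)

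- At p = 0.05: 0.2573×0.1530 + 0.0406×0.5123 + 0.0038×1 = 0.064. Type I error is 6.4%.
- Early stop at p = 0.05: 0.95^7 = 0.698, matching the stated 70%.
- At p = 0.30: 0.2471×0.9525 + 0.3177×0.9932 + 0.3529×1 = 0.904. Power is 90.4%.

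A search over designs also returns 0/7, 2/21 as the Simon optimal design for these inputs.

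**Type I error under the two readings of p0.** The loss fraction d is an assumption.

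- *p0 describes evaluable patients:* the rule is applied to the population it was designed for. Type I error is 6.4% at any d.
- *p0 describes all treated patients and every loss is a non-responder:* the rate among evaluable patients is 0.05/(1 − d).

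| d | Rate among evaluable | Early stop | Type I error |
|---|---|---|---|
| 0 | 5.00% | 69.8% | 6.4% |
| 10% | 5.56% | 67.0% | 8.2% |
| 17.6% | 6.07% | 64.5% | 10.0% |

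If lost patients instead respond at half the overall rate, 10% loss gives 7.3%, and the 10% limit is reached only at 30% loss.

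**What the accrual ceiling allows.** Section 10 plans 15 Phase I patients plus 36 new Phase II patients, with up to 6 carried over from Phase I, so 15 + 36 = 51 of 60 places are used and 9 are spare. With both cohorts full (42 evaluable), the largest pooled loss is 9/(42+9) = 9/51 = 17.6%. Without carry-overs, 60 − 15 − 42 = 3 places are spare and the pooled loss is at most 3/45 = 6.7%, giving 7.5% on the second reading. A single cohort could lose more, and so could the trial if a cohort stops early or Phase I uses fewer places.

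**The case against.** The strongest objection is that section 10 states 5% and 30% in the same design paragraph that counts evaluable patients. The natural reading is that both rates describe evaluable patients, and then type I error does not move. This stands. Section 10.1 does not overturn it, since it is a general sentence that names no competing population.

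Second, the documents expect few inevaluable patients, and the ceiling limits how many can be replaced. This also stands: with full cohorts the pooled loss can just reach the point where the less favorable reading hits 10%.

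Third, the progression-or-death clause, and the exception from replacement for deaths within 14 days, suggest that early failures were meant to count. That may well be the intent, but the opening and closing sentences say otherwise, so the objection shows that the section needs reconciling, not that it is sound.

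A reader might also infer that delayed patients are lost, because at 21-day intervals the fourth infusion falls on Day 1 + 3×21 = 64, after a Day 60 scan. The documents do not support this. Section 6.3 allows 2 weeks either side of 8 weeks, and section 3.1, section 3.1.2.1 and the study calendar tie restaging to the end of the fourth cycle or of the course.

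Finally, an all-treated primary analysis is a choice, and it is free of consequences for power only if 30% was an all-treated target. That condition is carried into the fix.

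**Conclusion.** The point holds as a defect in the definition of the primary response population, and it should be fixed. Followed as worded, section 10.2 removes almost only non-responders from the counts behind both decision rules, so with any such losses the ORR overstates the all-treated rate (14.3% against 11.5% in the example with 5 losses). The section also lets one patient be classified two ways.

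A reader might go further and infer that the trial's type I error exceeds its 10% limit. The documents do not show that. It would need the 5% null to describe all treated patients, essentially every loss to be a non-responder, and a loss above 17.6%. The first runs against the framing of section 10, and no document gives a loss rate. Section 1.3.4.1 reports that 7 of 12 patients were evaluable for response in the earlier trial of this drug, but that trial used a different schedule and the section gives no reasons for the rest. It does not establish a rate for this trial.

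**What to change.** In section 10.2:

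- Remove the 4-cycle precondition and the wording that limits progressors to toxicity evaluability.
- Define the primary response population in each cohort as all eligible patients who start mithramycin at the MTD, with a rule for Phase I carry-overs fixed before their response is known.
- Count a confirmed CR or PR as a response and everyone else as a non-responder, including early progression, death, withdrawal or no post-baseline scan. Do not replace patients for response.

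Use the same denominator in sections 10 and 10.1, and align section 2.4. Keep the 0/7 and 3-or-more-in-21 rules. Report ORR among patients who complete 4 cycles as secondary. State which population the 5% and 30% rates describe. The rule for taking patients off treatment is not changed.

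The cost is wording, with no added patients. With losses kept in the denominator, type I error against an all-treated 5% is 6.4%. If 30% was meant as a rate among completers, the all-treated rate is 0.30 × (1 − d), and power under the same rule is 86.4% at 10% loss (rate 0.27) and 80.9% at 20% loss (rate 0.24). In that case, restate the power rather than enroll more patients.

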10.3 SECONDARY ENDPOINTS

Pharmacokinetic analysis will be conducted using non-compartmental methods. For pharmacodynamic endpoints, descriptive statistics will be used for each endpoint. Briefly, pharmacokinetics and molecular endpoints in target tissues will be assessed before and after mithramycin treatment, with the primary focus being comparison of microarray, qRT-PCR and IHC results relative to profiles identified in our preclinical studies. It is anticipated that non-parametric statistical methods will be used to compare paired results before and after treatment (but not between groups), as well as to perform comparisons or correlations among parameters. As the exact set of comparisons and analyses to be performed will be determined following

completion of the trials, and will be based on limited numbers of patients, the analyses will be considered exploratory and hypothesis generating rather than definitive. The results of these descriptive analyses will be used to design further studies.

11 HUMAN SUBJECTS PROTECTIONS

11.1 RATIONALE FOR SUBJECT SELECTION

The patients to be entered on this protocol have advanced malignancies involving lungs, esophagus, or pleura and have limited life expectancies. This population was selected because of the unknown outcome of this treatment in terms of its effectiveness. The experimental treatment has a chance to provide clinical benefit although this is unknown. Subjects of both genders and all racial/ethnic groups are eligible. Efforts will be made to extend accrual to a representative population, but in this preliminary study, a balance must be struck between patient safety considerations and limitations on the number of individuals exposed to potentially toxic and/or ineffective treatments on the one hand and the need to explore gender and ethnic aspects of clinical research on the other hand. If differences in outcome that correlate with gender or ethnic identity are noted, accrual may be expanded, or a follow-up study may be written to investigate these differences more fully. One strategy for recruitment may be to distribute an IRB approved protocol recruitment letter to General and Oncology physicians and nurses.

11.2 PARTICIPATION OF CHILDREN

It is anticipated that most children with cancer will not have disease that is appropriate for study. Because the effects of mithramycin have not been evaluated in children, individuals <18 will be excluded from this study until more data are available.

11.3 PARTICIPATION OF SUBJECTS UNABLE TO GIVE CONSENT

Adults unable to give consent are excluded from enrolling in the protocol. However, re-consent may be necessary and there is a possibility, though unlikely, that subjects could become decisionally impaired. For this reason and because there is a prospect of direct benefit from research participation (Section 11.4), all subjects \geq age 18 will be offered the opportunity to fill in their wishes for research and care, and assign a substitute decision maker on the “NIH Advance Directive for Health Care and Medical Research Participation” form so that another person can make decisions about their medical care in the event that they become incapacitated or cognitively impaired during the course of the study. Note: The PI or AI will contact the NIH Ability to Consent Assessment Team (ACAT) for evaluation as needed for the following: an independent assessment of whether an individual has the capacity to provide consent; assistance in identifying and assessing an appropriate surrogate when indicated; and/or an assessment of the capacity to appoint a surrogate. For those subjects that become incapacitated and do not have pre-determined substitute decision maker, the procedures described in Policy 403 for appointing a surrogate decision maker for adult subjects who are (a) decisionally impaired, and (b) who do not have a legal guardian or durable power of attorney, will be followed.

11.4 EVALUATION OF POTENTIAL BENEFITS AND RISKS

The risks and benefits of participation for adults who become unable to consent on study are no different than those described for the rest of the study population.

11.4.1 Risks

11.4.1.1 Blood Sampling

Side effects of blood draws include pain and bruising, lightheadedness, and rarely, fainting.

11.4.1.2 Urine Collection

There is no physical risk involved with urine collection.

11.4.1.3 Ultrasound and EKG

No risks are associated with these procedures. The patient may experience minimal discomfort during the procedure.

11.4.1.4 Pulmonary Function Tests

These tests are safe and side effects are unlikely, but may include brief light headedness or slight soreness of the chest.

11.4.1.5 Study Drug Risks

The risks to the patient participating in this trial are anticipated to be small and are primarily the risks associated with administering the study drug.

These potential risks and benefits will be carefully discussed with the patient at the time consent is obtained. Patients will be monitored throughout the study in order to limit the consequences of any adverse events.

11.4.1.6 Central Line

IV drugs on this study will be given through a central line, a “tunneled” catheter surgically inserted into one of the main blood vessels leading to the heart. The risks associated with the procedure include pain, bleeding, infection, puncture of the underlying lung and pulmonary embolism. Lung puncture can result in lung collapse, which might require that a chest tube be placed into the chest cavity (usually for a day or two) to help the lung re-expand. The long-term risks of the catheter include infection and clotting of the vein in which the catheter sits which can break off and travel to the veins near the neck, face, chest, arms or lungs (pulmonary embolism).

11.4.1.7 Biopsy Risks

The risks associated with biopsies are pain and small amounts of bleeding at the biopsy site, and rarely, a small infection at the site. Biopsy sites usually heal very well and with very little scarring. In order to minimize pain, local anesthesia will be used; side effects of the local anesthesia may include a mild burning sensation when the numbing medicine is injected into the skin CT guidance will be used in obtaining biopsies.

11.4.1.8 Scans and Contrast

The most common discomfort is the length of time a patient must lay still during a scan. Patients may also become uncomfortable with the closed space of the machines.

There is a small risk of reaction in scans involving contrast. Common reactions include pain in the vein where the contrast was given, a metallic or bitter taste in the mouth, headache, nausea and a warm or flushing feeling that lasts from 1-3 minutes. In very rare cases, severe reactions that affect breathing, heart rhythm or blood pressure have occurred.

An IV line may need to be inserted for administration of the contrast agent or anesthetic, which may cause pain at the site where the IV is placed and there is a small risk of bruising or infection.

11.4.1.9 Risks of Exposure to Ionizing Radiation

This research study involves the potential for 6 CT CAP scans, 6 PET/CT scans as well as a potential maximum of 5 CT-guided biopsies (2 required, see [Appendix 2](#)) over the course of the first year on study. This radiation exposure is not required for medical care and is for research purposes only. Subjects will be exposed to approximately 17.8 rem. This amount of radiation is above the guideline of 5 rem per year and will expose the subject to the roughly the same amount of radiation as 59.3 years of background radiation.

11.4.2 Benefits

There may be some direct benefit to patients who participate in this trial since it is anticipated that mithramycin infusion may cause tumor stabilization or some tumor regression. The greatest benefit will be the information regarding the feasibility, toxicity and dosing of mithramycin administration, as well as the information on changes in cancer stem cell gene expression.

11.5 CONSENT PROCESS AND DOCUMENTATION

The informed consent document will be provided to the participant or consent designee(s) (e.g., the legally authorized representative [LAR] if participant is an adult unable to consent) for review prior to consenting. A designated study investigator will carefully explain the procedures and tests involved in this study, and the associated risks, discomforts and benefits. In order to minimize potential coercion, as much time as is needed to review the document will be given, including an opportunity to discuss it with friends, family members and/or other advisors, and to ask questions of any designated study investigator. A signed informed consent document will be obtained prior to entry onto the study.

The initial consent process as well as re-consent, when required, may take place in person or remotely (e.g., via telephone or other NIH approved remote platforms) per discretion of the designated study investigator and with the agreement of the participant/consent designee(s). Whether in person or remote, the privacy of the subject will be maintained. Consenting investigators (and participant/consent designee, when in person) will be located in a private area (e.g., clinic consult room). When consent is conducted remotely, the participant/consent designee will be informed of the private nature of the discussion and will be encouraged to relocate to a more private setting if needed.

12 PHARMACEUTICAL AND INVESTIGATIONAL DEVICE INFORMATION

12.1 MITHRAMYCIN (PLICAMYCIN)

Mithramycin is an antineoplastic antibiotic (oligosaccharide) produced by the growth of *Streptomyces argillaceus*, *S. plicatus* and *S. tanashiensis*. Previously used in the treatment of inoperable metastatic neoplasms of the testes, and for the symptomatic treatment of hypercalcemia and hypercalciuria.

12.1.1 Source

Mithramycin was supplied by IriSys LLC to the NIH Clinical Center Pharmacy, which will be providing the mithramycin under an IND held by the CCR.

12.1.2 Toxicity

The following effects have been observed in previous human administration (possible signs and symptoms in parentheses where appropriate)

More frequent:

- Hypocalcemia (muscle and abdominal cramps)
- Anorexia (loss of appetite)
- Diarrhea
- Stomatitis
- Nausea or vomiting —may occur 1 to 2 hours after initiation of therapy and continue for 12 to 24 hours

Note: Incidence and severity of *gastrointestinal side effects* may increase with too rapid a rate of administration.

Less frequent

- Drowsiness
- Fever
- Headache
- Mental depression
- Pain, redness, soreness, or swelling at injection site
- Unusual tiredness or weakness
- Gastrointestinal bleeding (bloody or black, tarry stools; vomiting of blood)
- hepatotoxicity (yellow eyes or skin)
- Epistaxis, hematemesis
- Leukopenia (sore throat and fever)—incidence about 6%
- Petechial bleeding
- Thrombocytopenia
- Toxic epidermal necrolysis (flushing or redness or swelling of face; skin rash)—possible early symptoms of overdose

Note: Hemorrhagic diathesis—Incidence more frequent with doses of more than 30 mcg (0.03 mg) per kg of body weight a day and/or for more than 10 doses.

